4.4.1.2 Main analytical approach

ITI success

The number and proportion of patients achieving complete ITI success, partial success, treatment failure, undetermined, or ongoing with ITI will be summarized.

The ITIFAS will be used for this analysis.

Occurrence of relapse after successful ITI

Occurrence of relapse will be summarized descriptively by calculating the proportions of patients who reach ITI success and later meet criteria of relapse during the Tapering Period, Follow-up Period, and the two Periods combined. The TPFAS will be used for this analysis.

Time to relapse will be defined as the duration between ITI success and time of relapse. Time to relapse from successful ITI will also be summarized descriptively for patients who relapsed during either the Tapering or Follow-Up Period.

Number of bleeding episodes during ITI, Tapering, and Follow-Up Periods

The number of bleeding episodes during ITI Period will be summarized by month using the ITIFAS. Descriptive statistics for annualized bleeding rate while the patients undergo ITI treatment will also be provided. The same analysis will be conducted by whether the bleeding episode is treated, and by type and location of bleeding episodes.

Patients will only be included in this analysis if they were observed for at least 90 days.

The annualized bleeding episodes will also be summarized for the Tapering and Follow-Up Periods using the TPFAS and by patient status of relapse. Detailed results based on whether a bleeding episode is treated, and type and location of bleeding episodes will also be provided.

Number of days away from work or school

If sample size permits ($n \geq 5$), number of days missed from school or work per month will be summarized descriptively for the ITI Period using the ITIFAS and for the combined Tapering and

Follow-Up Periods using the TPFAS. Otherwise, the data will be tabulated in individual patient listing only.

Number of hospitalization days

If sample size permits ($n \geq 5$), number of hospitalization days per year will be summarized descriptively for the ITI Period using the ITIFAS and for the combined Tapering and Follow-Up Periods using the TPFAS. Otherwise, the data will be tabulated in individual patient listing only.

Adherence

Percentage of administered doses as registered in the EPD and EDC versus the prescribed doses and percentage of number of days with infusions as registered in the EPD and EDC compared with the prescribed number of days will be summarized using descriptive statistics for each of the 3 periods separately.

[figure not shown]
Consumption during ITI

[figure not shown]
Refer to [Section 4.7.1](#).

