### 6.2. Secondary Objectives and Endpoints

The secondary objectives are as follows:

- To describe the outcome of ITI treatment
- To describe the relapse rate over the 48-week (12-month) period following successful ITI performed with rFVIIIFc
- To describe the intercurrent bleeding during the ITI Period and during the 48-week (12-month) period after successful ITI performed with rFVIIIFc
- To describe the safety and tolerability of rFVIIIFc when used for ITI
- To evaluate the impact of ITI treatment with rFVIIIFc on health economics and adherence

The secondary endpoints are as follows:

- ITI success
  - Confirmed negative titers consisting of 2 consecutive negative inhibitor assessments within 2 weeks ( $\pm 3$  days) based on local laboratory results  $<0.6$  BU/mL by the Nijmegen-modified Bethesda assay; determination of negative titer based on the Bethesda assay is acceptable at sites that have not yet adopted the Nijmegen-modified Bethesda assay
  - IR  $\geq 1.32$  IU/dL per IU/kg in 2 consecutive assessments representing  $\geq 66\%$  of the expected IR 2 IU/dL per IU/kg ([SmPC](#); [USPI](#))
  - $t_{1/2} \geq 7$  hours
- Occurrence of relapse (defined as confirmed positive inhibitor titer  $\geq 0.6$  BU/mL), abnormal recovery after tolerance is achieved, and  $t_{1/2} < 7$  hours) during the Tapering or Follow-Up Periods
- Number of bleeding episodes during the ITI Period and during the 48-week (12-month) period after successful ITI performed with rFVIIIFc
- Adverse events (AEs) and serious adverse events (SAEs)

[figure not shown]
CONFIDENTIAL

The information contained herein may not be used, disclosed, or published without the written consent of  
Bioverativ Therapeutics Inc.

Page 36

- Number of days away from work or school
- Number of hospitalization days
- Adherence (defined as percentage of administered doses versus planned doses)
- Consumption of rFVIIIFc (measured in total rFVIIIFc use)

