### **7.2.4. Tapering Period**

Subjects who have met the criteria for ITI success will enter the Tapering Period. Further details about the recommended dosing regimen for tapering are described in Section 11. Subjects with bleeding episodes during the Tapering Period will be tested for recurrence of inhibitors and monitored for relapse.

During the Tapering Period, treatment with bypassing agents may be considered if bleeding is unresponsive to treatment with rFVIIIFc (see Section 7.2.2.1). Testing for recurrence of inhibitors will be performed throughout the Tapering and Follow-Up Periods.

Subjects will visit the clinic 2 and 4 weeks after the first visit in the Tapering Period and then every fourth week for a minimum of 16 weeks (4 months). The duration of the Tapering Period may be modified by the Investigator with the Sponsor Medical Monitor's approval based on the subject's clinical response. If the Tapering Period exceeds 16 weeks (4 months), unscheduled visits will be performed every 4 weeks (1 month) or per the Investigator's judgment.

During the Tapering Period, subjects will undergo procedures and assessments at designated visits per the schedule of events (see Table 2). At each visit, samples for inhibitor titer and IR assessments will be drawn and sent to the local and central laboratories to monitor for relapse.

If the subject experiences bleeding during the Tapering Period, the treatment of the bleeding will be left to the discretion of the Investigator. During the Tapering Period, treatment with bypassing agents may be considered if bleeding is unresponsive to treatment with rFVIIIFc (see Section 7.2.2.1).

Throughout the Tapering Period, rFVIIIFc administration, bypassing agent administration, and any bleeding episodes will be collected by the subject and/or his caregiver in the EPD. The EPD data will be reviewed by the Investigator on an ongoing basis and discussed with the subject at each visit.

CONFIDENTIAL

The information contained herein may not be used, disclosed, or published without the written consent of Bioverativ Therapeutics Inc.

Page 44

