#### Occurrence of relapse after successful ITI

Occurrence of relapse will be summarized descriptively by calculating the proportion of subjects with ITI success who reach the criteria for relapse. The TPFAS will be used for this analysis.

Time to relapse will be defined as the duration between ITI success and time of relapse. Time to relapse from successful ITI will also be summarized descriptively for subjects who relapsed during the Tapering or Follow-Up Period.

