3 ANALYSIS POPULATIONS

For the purpose of statistical analyses, 3 analysis sets are defined based on the following criteria:

Table 2 - Populations for analyses

Population	Description
ITI full analysis set (ITIFAS)	This set will include all patients who received at least 1 infusion of rFVIIIFc. All analyses describing efficacy and safety during the ITI treatment period will be based on this analysis set. This analysis set will also be used for analysis of endpoints which summarize cumulative results from ITI, tapering, and follow-up periods.
Tapering period full analysis set (TPFAS)	This set will include all patients who entered the tapering period of the study. All analyses describing efficacy and safety during this study phase will be based on this analysis set. This analysis set will also be used for analysis of endpoints which summarize cumulative results from tapering and follow-up periods.
Follow-up period full analysis set (FUPFAS)	This set will include all patients who entered the follow-up period of the study. All analyses describing efficacy and safety during this study phase will be based on this analysis set.

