4 STATISTICAL ANALYSES

4.1 GENERAL CONSIDERATIONS

Continuous data will be summarized using the number of observations available, mean, standard deviation (SD), median, minimum, and maximum. The 25th (Q1) and 75th (Q3) percentiles and 95% confidence intervals may be presented where appropriate. Categorical and ordinal data will be summarized using the count and percentage of patients.

In general, event time variables will be summarized in two ways. For the subset of patients who experience the event of interest, the data will be summarized using standard descriptive statistics for continuous variables as described above. In addition, Kaplan-Meier estimates will be provided for ITI full analysis set regardless whether a patient experiences the event of interest. Patients who do not reach an event will be censored on the date of the last on-study follow-up visit unless otherwise specified in the SAP.

The baseline value is defined as the last available value before the first dose of ITI with rFVIIIFc.

Unless otherwise specified, analyses will be performed for all treated patients.

Observation period

The observation period will be divided into 3 segments:

- **ITI period** starts on the day of the first dose of ITI with rFVIIIFc. For those who successfully tolerized and entered the tapering period, the end of the ITI period is the day before the first visit of the tapering period. For those who did not successfully tolerate per protocol, the end of the ITI period is the day of the last study visit.
- **Tapering period** starts on the day of first visit of the tapering period and ends on the day of the last visit of the tapering period. For those who did not enter the follow-up period, the tapering period ends on the day of the last study visit.
- **Follow-up period** starts on the day after the last visit of the tapering period and ends on the day of the last study visit.

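### Relapse is planned as a crude proportion with no 48-week horizon or censoring, so it may differ from the 48-week relapse rate in the objective; a Kaplan-Meier estimate in the TPFAS would be a cheap addition

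*SAP*

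**What the plan says.** - **Objective** (Protocol 6.2, repeated in SAP Table 1): "To describe the relapse rate over the 48-week (12-month) period following successful ITI performed with rFVIIIFc".
- **Relapse statistic** (SAP 4.4.1.2): relapse is summarized by "calculating the proportions of patients who reach ITI success and later meet criteria of relapse during the Tapering Period", and likewise for Follow-Up and the two periods combined. The set is explicit: "The TPFAS will be used for this analysis". SAP Section 3 defines it: "This set will include all patients who entered the tapering period of the study". Only ITI successes enter tapering.
- **Time to relapse** (SAP 4.4.1.2): "Time to relapse from successful ITI will also be summarized descriptively for patients who relapsed during either the Tapering or Follow-Up Period". Protocol 16.2.2.2 agrees: it is "summarized descriptively for subjects who relapsed during the Tapering or Follow-Up Period". SAP 4.4.1.1 starts the clock at the date of ITI success.
- **General rule for event times** (SAP 4.1): besides descriptive statistics in those with the event, "Kaplan-Meier estimates will be provided for ITI full analysis set regardless whether a patient experiences the event of interest". The rule is introduced as applying in general. Section 4.4.1.2 neither repeats nor cancels it for relapse.
- **Length of observation**: Protocol 7.2 sets a minimum taper of 16 weeks and no maximum. Protocol 7.2.4 allows a longer one: "If the Tapering Period exceeds 16 weeks (4 months), unscheduled visits will be performed every 4 weeks". Protocol 7.2.5 gives 32 weeks of Follow-Up after tapering is completed. Table 2 puts the EOT Visit at Week 48 (±2 weeks) after ITI success, or at relapse.

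**The concern.** The objective names a fixed window; the planned statistic does not. A success who withdraws at Week 16 stays in the denominator and counts the same as one observed relapse-free to Week 48. A relapse after Week 48 in a patient with a long taper would count in full.

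Unequal observation is foreseeable. Protocol Section 10 requires withdrawal for several reasons without replacement, and 7.4 lets the sponsor stop the study. SAP 4.9 allows further interim analyses, but the ongoing category in SAP 4.4.1.1 covers ITI outcome only, so successes still under observation would count as relapse-free. Protocol 16.2.2.2 annualizes bleeding because the Tapering and Follow-Up Periods may differ in length, yet makes no such allowance for relapse.

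The one place that would supply a censored estimate, SAP 4.1, names a set that does not suit this endpoint. A programmer must either omit the estimate or run it on patients who have no start date. The default censoring date there, the last on-study follow-up visit, does not fit either: Table 2 schedules no titer or IR at the Final Safety Follow-Up.

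**Working it through.** The documents give no relapse rate, dropout rate or precision figure, so the risks, dropout rates and extended durations below are assumptions.

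**1. The plan's own window.** Minimum taper 16 + Follow-Up 32 = 48 weeks, matching the objective and the EOT week. The match holds only at a 16-week taper. With a taper of 24 or 32 weeks, Protocol 7.2.5 gives 24 + 32 = 56 or 32 + 32 = 64 weeks. Under Table 2 the window stays at 48 and Follow-Up shrinks to 48 − 24 = 24 or 48 − 32 = 16 weeks.

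**2. Expected crude proportion with dropout.** Take constant relapse rate λ and dropout rate μ, where p is the 48-week relapse risk, d is the 48-week dropout, λ = −ln(1−p)/48 and μ = −ln(1−d)/48. Observed to week T:

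expected crude = λ/(λ+μ) × [1 − exp(−(λ+μ)T)]

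For p = 20%, d = 30%, T = 48: 0.2231/(0.2231 + 0.3567) × [1 − 0.8 × 0.7] = 0.3849 × 0.44 = 16.9%.

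| Dropout by Week 48 | Expected crude value, true 48-week risk 20% |
|---|---|
| 0% | 20.0% |
| 10% | 19.0% |
| 20% | 18.0% |
| 30% | 16.9% |
| 40% | 15.8% |

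**3. Longer observation, no dropout.** Expected crude = 1 − 0.8^(T/48): 22.9% at T = 56 and 25.7% at T = 64.

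**4. Small worked examples, 10 successes each.**
- Relapses at Weeks 12 and 40; withdrawals at Weeks 8, 16 and 28; five followed to Week 48. Crude 2/10 = 20.0%. Kaplan-Meier at 48 weeks: 9 at risk at Week 12 and 6 at Week 40, so 1 − (8/9)(5/6) = 25.9%.
- Same relapses, no withdrawals: crude 20.0%, Kaplan-Meier 20.0%.
- Relapses at Weeks 12 and 58, the second after an extended taper, no withdrawals: crude 20.0%, Kaplan-Meier at 48 weeks 1 − 9/10 = 10.0%.

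**5. Precision.** Protocol 5.1 cites ITI success rates of 33% to 88%. With up to 17 subjects (Protocol 16.1), that is 0.33 × 17 = 5.6 to 0.88 × 17 = 15.0, about 6 to 15 successes. SAP Section 2 still says up to 30, which would give 9.9 to 26.4. The exact 95% CI for 2/10 is 2.5% to 55.6%.

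**The case against.** **The planned summary is legitimate.** The trial is descriptive, with no hypothesis tests (Protocol Section 16). If every success is followed to relapse or Week 48, the crude proportion equals the Kaplan-Meier value, as the second example in step 4 shows. SAP 4.3.4 lists relapse status, period durations and time from success to relapse for each patient, so a reader could rebuild the estimate. This stands, and it is why the planned proportion is not an error. Listings still do not prespecify the 48-week figure.

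**The ITIFAS is not the relapse set.** A reader might infer from SAP 4.1 that never-tolerized patients dilute the relapse rate. The documents do not support that. SAP 4.4.1.2 names the TPFAS for the proportion, and an ITIFAS relapse curve is only implied by a general rule. Patients without an ITI success date have no clock on which to stay at risk; if they are dropped or censored at time zero, the 25.9% in step 4 is unchanged. What remains is an instruction that cannot be applied as worded.

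**The window need not exceed 48 weeks.** A reader might infer that a long taper always lengthens it. Table 2 counts its visits from ITI success, and the stated maximum duration of about 2 years fits 4 + 48 + 48 + 2 = 102 weeks better than 4 + 48 + 56 + 2 = 110. But 7.2.5 reads the other way, so the conflict remains.

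**Kaplan-Meier has its own assumption.** Some withdrawal reasons in Protocol Section 10, such as use of another FVIII product or Investigator judgment, may be related to impending relapse. Censoring would then be informative. This stands as a caveat on the proposed estimate.

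**Conclusion.** The point holds as an inexpensive improvement. The plan does not specify the 48-week relapse rate that the objective names, and the crude figure can miss it in either direction. At an assumed true risk of 20%, it falls about 1 to 4 points for 10% to 40% dropout and rises about 3 to 6 points for observation to 56 or 64 weeks. These sizes rest on constant rates, dropout unrelated to relapse, and assumed dropout and durations. They are small beside an interval such as 2.5% to 55.6%. It would go too far to say that the 48-week rate will not be estimated: that depends on withdrawals, interim cuts and tapering length. Two textual matters need settling whatever the size: which set a relapse Kaplan-Meier estimate would use, and when observation ends after a taper longer than 16 weeks.

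**What to change.** In SAP 4.4.1.2:
- Keep the crude count and proportion in the TPFAS.
- Add the Kaplan-Meier cumulative relapse proportion at 48 weeks from ITI success, in the TPFAS, with a 95% CI. State how the ±2-week EOT window is handled, so that a relapse found at a late EOT Visit is not lost.
- Censor at the last titer/IR assessment, not at the last visit of any kind.
- Name the one assessment that dates a relapse. Protocol 7.2.4 requires two consecutive assessments 2 to 4 weeks apart, and the SAP does not say which supplies the date.
- State that this overrides the ITIFAS rule in SAP 4.1 for time to relapse.

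In the Protocol, reconcile 7.2.5 with Table 2 on the end of observation when tapering exceeds 16 weeks.

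The cost is a few lines of SAP wording, one protocol clarification and one extra output. The downside is a wide interval from few events.

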The information contained herein may not be used, disclosed, or published without the written consent of Bioverativ Therapeutics Inc.

Page 27

Activities	Tapering Period 	Follow-Up Period 	EOT 	
	Tapering Initiation Visit/Telephone Call,  Week 2, 4, 8, 12, and 16 Visits	Week 28 and 40 Visits 	EOT Visit	Final Safety Follow-Up
	Starting at ITI success and continuing for a minimum of 16 weeks with visits after 2 weeks ( $\pm 3$ days), 4 weeks ( $\pm 1$ week), and then every 4 th week ( $\pm 1$ week)	Week 28 and 40 visits ( $\pm 2$ weeks)  following ITI success	Week 48 visit ( $\pm 2$ weeks) following ITI success OR upon relapse	7 to 14 days after EOT Visit
Concomitant Therapy/ Procedures Recording	X	X	X	X

Abbreviations: EOT=End of Treatment; EPD=electronic patient diary; ET=early termination; FVIII=coagulation factor VIII; IR=incremental recovery; ITI=immune tolerance induction; PK=pharmacokinetic; rFVIIIFc=recombinant coagulation factor VIII Fc fusion protein;  $t_{1/2}$ =half-life.

NOTE: inhibitor titer, FVIII activity level,  $t_{1/2}$ , and IR are all assessed at the local laboratory, with confirmation by the central laboratory. The Investigators will use local laboratory results for decision-making purposes.

Hematology, blood chemistry, and urinalysis are assessed only at the local laboratory.

- 1 During the Tapering and Follow-Up Periods, the subject's dose will be adjusted to achieve each subject's prophylactic dose as determined by the Investigator. Minimum Tapering Period is 16 weeks (4 months). Subjects who relapse during the Tapering Period (i.e., who have confirmation of inhibitor development AND who have confirmed decrease of IR, with or without clinical signs or symptoms) will proceed immediately to the EOT Visit. Subjects will be closely monitored during the Tapering Period for potential relapse.  
For Canada specific requirements: see Appendix B.
- 2 Timing of the EOT Visit will vary for subjects, as described in Section 7.2.6.

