### **16.2. Efficacy**

#### **16.2.1. Analysis Populations**

For the purpose of statistical analyses, 3 analysis sets are defined based on the following criteria:

- ITI Full Analysis Set (ITIFAS): This set will include all subjects receiving at least 1 infusion of rFVIIIFc. All analyses describing efficacy and safety during ITI treatment will be based on this analysis set.
- Tapering Period Full Analysis Set (TPFAS): This set will include all subjects entering the tapering phase of the study. All analyses describing efficacy and safety during this phase will be based on this analysis set.
- Follow-Up Period Full Analysis Set: This set will include all subjects entering the follow-up phase in the study. All analyses describing efficacy and safety during this phase will be based on this analysis set.

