Partial success is defined as achieving negative inhibitor titer and one of the PK parameters of ITI success: IR ≥ 1.32 IU/dL per IU/kg OR $t_{1/2} \geq 7$ hours.

Patients who have been determined to have achieved only partial success will then proceed to EOT Visit.

Ongoing

This category is only applicable for the interim analysis for the patients who do not meet the definitions for the 4 categories of ITI outcomes as described above. For patients who are ongoing, their status will be further categorized into:

- Positive inhibitor titer
 - Inhibitor titer reduced ($\geq 20\%$) from baseline but not yet negative
 - Inhibitor titer remains the same ($\pm 20\%$) as baseline
 - Inhibitor increased ($\geq 20\%$) from baseline
- Negative inhibitory titer
- Negative inhibitory titer and normal IR

The ITIFAS will be used for this analysis.

Occurrence of relapse after successful ITI

Occurrence of relapse is defined as the proportions of patients who reach ITI success and later meet criteria of relapse during the Tapering Period, Follow-up Period, and the two Periods combined.

Relapse

Relapse is defined as confirmed positive inhibitor titer ≥ 0.6 BU/mL and IR < 1.32 IU/dL after tolerance is achieved, during the Tapering or Follow-Up Periods. The samples for IR derivation need to meet the criteria of 24-hour wash-out period.

Results from local lab will be used for this determination. In the event that the local lab results are not available, the results from the central lab will be used. Occurrence and dates of positive inhibitor titer and loss of normal IR will be recorded in the eCRFs by the investigator.

Time to Relapse

This is defined as the number of days from the date of ITI success to the date of the first confirmed case of relapse.

Number of bleeding episodes

Annualized rate of the number of bleeding episodes during ITI Period will be calculated for each patient in the ITIFAS who had been observed for at least 90 days:

$$\text{annualized bleeding rate} = \frac{\text{number of bleeding episodes}}{(\text{length of study period in days}/365.25)}$$

Bleeding Episode

If a break-through bleed is not resolved right away, a patient may make multiple reports of the same bleed. To determine if multiple reports of bleeds belong to the same bleeding episode, the following definition is to be used.

Bleeds which receive treatment(s)

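### The SAP puts the Follow-Up-only relapse proportion on the TPFAS, although its own analysis-set rule assigns follow-up-phase efficacy to the FUPFAS

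*SAP*

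**What the plan says.** SAP 4.4.1.2, under occurrence of relapse after successful ITI, asks for three proportions, "during the Tapering Period, Follow-up Period, and the two Periods combined. The TPFAS will be used for this analysis".

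SAP section 3, Table 2, defines the sets:

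- TPFAS: "This set will include all patients who entered the tapering period of the study". Its use beyond the tapering phase is limited to one case: "This analysis set will also be used for analysis of endpoints which summarize cumulative results from tapering and follow-up periods".
- FUPFAS: "This set will include all patients who entered the follow-up period of the study. All analyses describing efficacy and safety during this study phase" are to be based on it.

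Protocol 16.2.1 defines the follow-up set in the same way ("This set will include all subjects entering the follow-up phase in the study") and also bases that phase's efficacy and safety analyses on it.

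The endpoint definition in SAP 4.4.1.1 reads: "Occurrence of relapse is defined as the proportions of patients who reach ITI success and later meet criteria of relapse during the Tapering Period", and continues with the Follow-Up Period and both periods combined. It gives no separate denominator for Follow-Up.

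Protocol 16.2.2.2 plans a single relapse proportion on the TPFAS, with no split by period.

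**The concern.** A proportion for the Follow-Up Period alone describes efficacy in that phase and does not accumulate results over two periods. By the SAP's own Table 2 it belongs on the FUPFAS, but SAP 4.4.1.2 puts it on the TPFAS without stating an exception.

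The two sets can differ. Under Protocol Table 2, footnote 1, a patient with confirmed relapse in Tapering "will proceed immediately to the EOT Visit", so he does not go on to Follow-Up. Protocol section 10 lists further reasons for leaving the study. SAP 4.1 provides for such patients: "For those who did not enter the follow-up period, the tapering period ends on the day of the last study visit". They stay in the TPFAS denominator of the Follow-Up figure although they cannot contribute a Follow-Up relapse.

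At stake is how the figure will be read. Someone who knows Table 2 will take a Follow-Up relapse proportion as the risk among patients followed in that period. The planned figure is something else, and nothing in its description says so.

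**Working it through.** **Nothing to reproduce.** The documents give no expected relapse rate and no precision or power calculation for this endpoint. Protocol section 16 rules out formal hypothesis testing. The check is direct arithmetic on the denominator.

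**Inputs**

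- T = patients in the TPFAS. Not given. Planned enrolment is an upper bound: up to 17 in Protocol 16.1 (SAP section 2 says up to 30).
- a = TPFAS patients who never enter Follow-Up. Not given; assumed.
- r = relapses in Follow-Up. Not given; assumed.

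**Formulas**

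- Follow-Up proportion as planned (TPFAS): r/T
- Follow-Up proportion under SAP Table 2 (FUPFAS): r/(T − a)
- Planned figure divided by FUPFAS figure: (T − a)/T

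The ratio never exceeds 1. The two figures differ only when a ≥ 1 and r ≥ 1. Enumerating all combinations for T = 1 to 17 gave no exception to either statement.

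**Illustrations (all counts assumed)**

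| T | a | r | TPFAS | FUPFAS | Factor |
|---|---|---|---|---|---|
| 17 | 2 | 1 | 1/17 = 5.9% | 1/15 = 6.7% | 0.88 |
| 12 | 1 | 1 | 1/12 = 8.3% | 1/11 = 9.1% | 0.92 |
| 12 | 3 | 1 | 1/12 = 8.3% | 1/9 = 11.1% | 0.75 |
| 12 | 3 | 2 | 2/12 = 16.7% | 2/9 = 22.2% | 0.75 |
| 9 | 3 | 2 | 2/9 = 22.2% | 2/6 = 33.3% | 0.67 |
| 12 | 0 | 1 | 1/12 = 8.3% | 1/12 = 8.3% | 1.00 |
| 12 | 3 | 0 | 0% | 0% | no difference |

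**Effect on the other two proportions.** None. The Tapering figure belongs on the TPFAS. The combined figure is cumulative, so the TPFAS is right for it under SAP Table 2, and it matches Protocol 16.2.2.2.

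**Additivity.** Suppose T = 12, with 2 relapses and 1 withdrawal in Tapering (a = 3) and 1 relapse in Follow-Up. On the TPFAS throughout, 2/12 + 1/12 = 3/12, that is 16.7% + 8.3% = 25.0%, the combined figure. With the FUPFAS for Follow-Up, 16.7% + 11.1% = 27.8%, which is not the combined 25.0%.

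**How the SAP treats other by-period results.** SAP 4.7.1 summarizes consumption and adherence for each period on that period's own set, and the last Follow-Up prophylactic doses on the FUPFAS. SAP 4.4.1.2 uses the TPFAS for work or school days and hospitalization days with the two periods combined. The Follow-Up relapse figure departs from this pattern. A likely explanation is that the protocol's single TPFAS proportion was split by period in the SAP and the set was not revisited, but the documents do not say so.

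**The case against.** The best defence starts from SAP 4.4.1.1. The population named there is patients who reach ITI success, and only they enter Tapering, so it is essentially the TPFAS. On that reading r/T is the share of all ITI successes whose relapse falls in Follow-Up. That is a legitimate quantity. It adds to the Tapering share to give the combined figure, and it fits an objective counted over the 48 weeks after successful ITI. An endpoint-specific assignment may also reasonably override a general rule. All of this stands as a reading. But the SAP neither labels the figure as such a share nor states an exception to Table 2.

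A reader might infer more than the documents support, in two ways.

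- *That the plan simply understates the true Follow-Up relapse proportion.* There is no single true proportion here: share of all successes and risk among those who entered Follow-Up are different questions. The planned figure is low only against the second, and only if both a and r are at least 1.
- *That heavy early relapse would be concealed and late durability made to look better.* The Tapering and combined proportions are reported alongside. SAP 4.2 reports the size of each analysis set, and SAP 4.3.4 requires a patient listing with time in each period, relapse status and time to relapse. The FUPFAS figure could be recomputed from planned output. Nor do the documents single out the Follow-Up-only proportion as the measure of durability.

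It is also fair to say that the difference is small beside sampling uncertainty: the exact 95% intervals for 1/12 and 1/9 are about 0.2% to 38% and 0.3% to 48%.

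**Conclusion.** The conflict between SAP 4.4.1.2 and SAP Table 2 (with Protocol 16.2.1) holds on the text and does not depend on any assumed count. The direction is also certain: the planned Follow-Up figure can equal the proportion among patients who entered Follow-Up or fall below it, never exceed it. Whether it falls below, and by how much, depends on how many patients miss Follow-Up and how many relapse there. The documents give neither number, and every percentage above rests on assumed counts.

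The consequence is limited. One of three components of a descriptive secondary endpoint is affected; the primary endpoint is untouched and no test depends on it. This is a minor correction, worth making because it is cheap and gives the Follow-Up figure a denominator of patients at risk of the event.

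**What to change.** In SAP 4.4.1.2, keep the TPFAS for the Tapering and combined relapse proportions, assign the FUPFAS to the Follow-Up proportion, and print numerator and denominator beside each. If the additive share on the TPFAS is also wanted, present it as a second figure, label it as the share of all TPFAS patients whose relapse fell in Follow-Up, and state that it is an exception to Table 2.

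The cost is about one sentence in the SAP and one denominator in a table; no new data are needed. There are two downsides. The Follow-Up figure may look less favourable, and with different denominators the period proportions no longer add up to the combined one. A footnote giving the denominators deals with the second.
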